9.7.6. Secondary Analyses

The following secondary analyses will be conducted:

- The cumulative incidence, CI(t), of events at time t will be estimated using the incidence density at that time, ID(t), in the equation CI(t)=1-exp^{-ID(t)*t}. Each point of the graph provides the cumulative incidence after t years of follow-up in the study, expressed as a percentage.
- A Cox proportional model will be adapted to multiple unordered events: the Time-varying covariates will be used, this technique is acceptable for unordered events (events can occur in any order). The cluster term will be used to compute a robust variance for the model. The term cluster(id) where each value of id is unique produces an approximate jackknife estimate of the variance. If the id variable is not unique, but identifies clusters of correlated observations, then the variance estimate is based on a grouped jackknife. The model will be used according to the following notes:
 - 1- Time-varying covariates will need to replace one record by n records, such as each new record describes a time-slice where covariates are fixed (inter-visit periods). Each such record remains independent while the endpoint occurrence only happens once (single event). If multiple events occur during the follow up, the time-slices are not independent for the same patient, thus the covariance between each row must be accounted by using sandwich robust variance cluster option. This technique is acceptable for unordered events (events can occur in any order). The cluster term is used to compute a robust variance for the model (approximate jack knife estimate).
 - 2- Time-varying effect means that PH is not constant in time. The major assumption of CPH is the lack of interaction of the covariates with time. This will be tested in the Schoenfeld test, on each covariate. If one or more covariate provides evidence of interaction with time, strata(variable) where variable is categorical, allows to model baseline F(t) calculated separately for each category of the variable.
 - 3- The model will be built both in stratifying with and without regrouped center and country.

9.7.6.1. *Effectiveness analysis*

All effectiveness parameters (ESS, MWT/MSLT and Fatigue Severity Scale) will be described at inclusion, six months after inclusion (only ESS scale) and every year until the end of the study, on the study population overall and by treatment group (OZAWADE® vs. non-OZAWADE®). Changes from inclusion may be calculated if relevant.

9.7.6.2. *Adherence*

The adherence to OZAWADE® assessed by the MMAS-8 questionnaire will be described at six months and then every year until end of the study. The adherence will be presented in terms of:

- Total score (0 − 8)
- Level of adherence (Low: < 6 / Medium: [6; 8[/ High: 8)

Adherence to continuous positive airway pressure (CPAP) will also be collected and described.

9.7.7. Other Safety Analyses

Adverse Events (AEs) will be coded with the Medical Dictionary for Regulatory Activities (MedDRA), version 25.1 or higher.

Firstly, incidences of all AEs, SAEs, AESIs (defined as cardiovascular events), and AEs related to study treatment will be described by treatment group (OZAWADE® vs. non-OZAWADE®) and overall by System Organ Class (SOC) and Preferred Term (PT).

To compute incidences, if a patient reported several AEs of a same PT in the period, only one AE will be counted. Denominator will then be the total number of patients and numerator will be the number of patients who reported at least one AE of the PT. Frequencies and percentages will be provided in the table.

More details on the types of events that will be described by SOC and PT and on listings that will be presented will be provided in the SAP.

Moreover, ECG results, blood pressure and heart rate will be described at each collection time by treatment group (OZAWADE® vs. non-OZAWADE®) and overall on the study population. The depression scale total score will also be described at each collection time except at the 6-month follow-up visit. Changes from inclusion may be calculated if relevant.

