9.3.7. Exposure and adherence to OZAWADE®

9.3.7.1. Treatment exposure

Exposure to OZAWADE® will be collected at inclusion and at follow-up visits (if not started at inclusion), with the date of prescription and the prescribed dose.

At each follow-up visit, dose modifications, treatment interruptions and permanent discontinuation will be collected. Reasons of changes will also be collected.

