9.7.5. Primary Analyses

The main objective of the study is to demonstrate that OZAWADE® supplementation does not increase CV events compared with control (non-inferiority). The following analysis will be conducted:

The annual CV morbidity incidence will be estimated by the occurrence of CVE per patient per year equivalent to the proportion of patients with at least one CVE.

The CV risk is known to be higher for OSA patient with existing CV history, using or not CPAP, and well-known risk factors: diabetes, cholesterol, weight, hypertension, demographics (age, gender), lifestyle (fitness, alcohol use, smoking habits).

A generalized linear mixed model featuring Poisson regression will be based on a post stratification model based on the following fixed covariates or random effects:

- nCVE_b, prior CV history measured by the number of CV events experienced before baseline, expected as the essential predicting covariates;
- Risk factors (RF): diabetes, cholesterol, weight, hypertension, alcohol use, and smoking habits reported at baseline;
- Demographics: gender, age, country, study center
- Matched classes propensity clusters: the treatment will be non-randomized but determined by the investigator, involving an expected imbalance between groups on baseline conditions. The decision of prescribing a given medicine will be assumed on a set of baseline covariates defined in the statistical plan. As too many covariates are expected, finding sufficient exact matches is unfeasible, and the goal of subclassification is to form matched subclasses (clusters), such that in each the distribution of covariates for the treated and control groups are as similar as possible. The propensity score will be used as the scalar distance with a two-stage algorithm starting with the nearest neighbour matching and optimized by a full matching procedure [39, 40, 41].

The final model is:

CVE ~ $nCVE_b + \Sigma_i RF_i + gender + age + trt + \{country\} + Offset (log-exp) + \{center | country\} + \{cluster\}$

The notation Σ_i RF_i covers the above mentioned considered risk factors. The obvious effect of the exposure duration is measured by the offset of its logarithm. The last fixed factor is the treatment (trt) binary effect (0=control, 1=pitolisant). Country, site effect nested within country, and cluster (matched group) effects will be used as random factors (between {}).

Sensitivity Analysis

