Site selection bias: Site involvement is voluntary and the final sample of participating sites may not be representative. This potential bias is inevitable in this type of study and its impact is difficult to evaluate. However, this bias will be minimized by the selection of a balanced number of centers in each participating country and by the fact that a feasibility study is on-going to identify physicians that could be interested in participating in the study. For this reason, refusal of few centers is not expected to have a significant impact on sites representativeness. The number of physicians solicited, having answered, having refused, having accepted, the number of sites initiated as well as the number of active sites will be presented. The reasons for refusal will be described.

Sampling bias: due to the exhaustive nature of the collection of subject data, the number of subjects may not be homogeneous between the sites and sites with a higher potential for recruitment may include more patients than others. However, to limit this bias a feasibility study is on-going to identify physicians that will be able to recruit a certain amount of patients. In addition, only physicians specialized in sleep medicine who receive, in medical consultation, OSA patients with diagnosis of excessive daytime sleepiness and who are likely to treat them with OZAWADE (sleep specialists, pulmonologists, cardiologists, otorhinolaryngologists and neurologists) will be selected.

Attrition bias: Patients lost to follow-up are the main source of attrition bias. Attrition can threaten sample representativeness if the patients lost to follow-up differ from the other patients in their baseline characteristics or in their outcomes. To decrease this bias, the centers will contact patients who did not attend their follow-up visits.

10. Protection of human subjects

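### Section 9.7.7 reports all-cause AEs and SAEs only as patient-count percentages, and no other analysis of them takes account of follow-up time, which will vary over five years

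*Protocol*

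**What the plan says.** Section 9.7.7 of the protocol states that "incidences of all AEs, SAEs, AESIs (defined as cardiovascular events), and AEs related to study treatment will be described by treatment group". It counts a patient once per preferred term and defines the proportion: "Denominator will then be the total number of patients and numerator will be the number of patients who reported at least one AE" of that term. On output it says "Frequencies and percentages will be provided in the table". No rate per unit of time is named. What it leaves to the SAP is narrower: "More details on the types of events that will be described by SOC and PT and on listings that will be presented will be provided" there. The denominator is therefore a stated rule and not an open detail.

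Elsewhere the protocol does use time at risk. In the primary Poisson model of section 9.7.5, "The obvious effect of the exposure duration is measured by the offset of its logarithm". Section 9.7.6 bases cumulative incidence on incidence density and adds a Cox model. Section 9.1.2.2 lists time to CVE, time to ADR and time to SADR as secondary endpoints.

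Section 9.7.2 makes every included patient eligible for analysis. Section 9.9 accepts that "Patients lost to follow-up are the main source of attrition bias". Section 9.3.7.1 provides for OZAWADE being started at a visit after inclusion.

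**The concern.** A proportion with a patient-count denominator gives a patient lost at month 3 the same weight as one followed for 60 months. If one group is observed for less time on average, it shows a lower percentage at the same underlying rate. A count denominator also cannot divide the time of a patient who starts OZAWADE after inclusion.

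For CVEs, which are this study's AESIs, and for ADRs and SADRs, a reader can turn to the time-based analyses. For AEs and SAEs regardless of causality, the 9.7.7 percentages are the only between-group information in the protocol. The ADR and SADR endpoints cannot stand in for them, because section 11.2.2 assesses causality only against OZAWADE, so never-exposed patients supply no real comparator rate. Section 8.1 makes long-term safety part of the primary objective, and section 7.2 names it as the missing information the study is meant to supply.

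**Working it through.** The plan states no figure on this point, so there is none to reproduce. The check has three steps.

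**1. Will follow-up vary between patients?** Inputs: two years of recruitment and five of follow-up (section 4); data collection from Q3/Q4 2024 to Q4 2030/Q1 2031 (section 6).

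- Needed for everyone to complete: 2 + 5 = 7 years.
- Longest window: 2031.25 − 2024.50 = 6.75 years. Shortest: 2030.75 − 2025.00 = 5.75 years.
- Most follow-up available to the last patient if enrolment takes the full two years: 6.75 − 2 = 4.75 years, or 5.75 − 2 = 3.75 years.

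So follow-up will be unequal between patients even before withdrawals and losses. Enrolment runs until the target is met in both groups (section 9.2.2.2). If the groups accrue at different speeds, their mean follow-up differs at the yearly interim reports and possibly at the end.

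**2. What does unequal loss do to the percentage?** The documents give no AE rate and no loss rate, so these are assumptions: constant AE hazard h, constant loss hazard d, five years.

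Observed proportion = h/(h+d) × (1 − exp(−5(h+d)))

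- h = 0.10, d = 0.10: 0.500 × (1 − exp(−1.00)) = 0.316
- h = 0.10, d = 0.03: 0.769 × (1 − exp(−0.65)) = 0.368

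The exposed/unexposed ratio when the true ratio is 1.00:

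| Loss per year, larger v smaller | Exposed group loses more | Unexposed group loses more |
|---|---|---|
| 8% v 4% | 0.92 | 1.09 |
| 10% v 3% | 0.86 | 1.16 |
| 15% v 5% | 0.81 | 1.23 |
| equal | 1.00 | 1.00 |

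If the true hazard ratio is 1.2 and the exposed group loses 10% v 3%, the exposed proportion is 0.12/0.22 × (1 − exp(−1.10)) = 0.364. Then 0.364/0.368 = 0.99, so the excess disappears from the table.

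Person-time at risk removes the shift. It is (1 − exp(−5(h+d)))/(h+d) per patient: 3.16 years at d = 0.10 and 3.68 years at d = 0.03. Then 0.316/3.16 = 0.368/3.68 = 0.10, or 10 per 100 patient-years in both groups.

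**3. The same question in terms of mean follow-up.** Proportion = 1 − exp(−rate × years), with equal true rates assumed anywhere from 0.02 to 0.20 per patient-year.

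| Mean follow-up, shorter v longer | Exposed group shorter | Unexposed group shorter |
|---|---|---|
| 4.5 v 5 years | 0.90–0.94 | 1.07–1.11 |
| 4 v 5 years | 0.81–0.87 | 1.15–1.24 |
| 5 v 5 years | 1.00 | 1.00 |

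A half-year gap therefore lowers the ratio by 6–10% and a one-year gap by 13–19% when the exposed group is the one followed for less time.

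**The case against.** A reader might infer that all safety comparisons, AESIs included, ignore time at risk. The documents do not support that. AESIs are the cardiovascular events, which have an offset, an incidence-density estimate and a Cox model; related and serious related events have time-to-event endpoints. A reader might also take the 9.7.7 tables for the study's main safety output. They appear under other safety analyses, are described without test or margin, and carry no formal conclusion.

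Nor do the documents show that follow-up will differ by group, or that any difference would favour the drug. Both groups share one visit schedule. Section 9.1.3 keeps patients who stop OZAWADE in the study, which removes the most obvious cause of shorter follow-up among the exposed, and it says AEs are still collected after withdrawal. Section 9.9 has centres contact patients who miss visits. These safeguards reduce differential loss. They do not deal with different accrual speeds under a short calendar, late starts of OZAWADE, or patients who cannot be traced.

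It can also be said that extra table columns are ordinary SAP content and that 9.7.7 excludes none. That is fair as far as it goes, but the denominator has been fixed in the protocol, and it is the only one named for all-cause AEs and SAEs.

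Finally, a rate per patient-year presumes a roughly constant hazard. If reactions cluster early, longer follow-up dilutes the rate. This stands, and it is the reason to keep the percentages.

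**Conclusion.** The point holds for all-cause AEs and all-cause SAEs: their only planned between-group summary takes no account of time at risk, in a study where follow-up will vary. The size depends on assumptions, since no AE or loss rate is given. At an AE hazard of 10% per year and loss of 10% v 3% per year, a null ratio reads 0.86 or 1.16 depending on which group loses more. It reads 1.00 if follow-up is equal. The distortion can hide an excess or create one; the documents do not say which is likelier, or that either will occur. The primary CVE comparison is not affected. This is a cheap improvement to descriptive tables, not a flaw in the main analysis.

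**What to change.** In section 9.7.7, add by group the first-event rate per 100 patient-years at risk with a 95% confidence interval, for all AEs and all SAEs, overall and by SOC and PT. Keep the crude percentages beside the rates.

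State how person-time is allotted when OZAWADE starts after inclusion: time and events before the start count as unexposed, and time and events after it as exposed. Without this, rates under unchanged group labels would still place some time in the wrong group.

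The cost is a few extra table columns. Section 9.3.7.1 already collects the prescription date, interruptions and permanent discontinuation, so no new exposure data are needed. Because the rates assume a roughly constant hazard, present them as a complement to the percentages and not as a replacement.

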9.1. Study design

9.1.1. Overall Design of the Study

This is a prospective, observational, multi-center, open-label, long term, cohort study (OZAWADE® exposed and OZAWADE® unexposed) designed to collect data on the long-term safety of OZAWADE® treatment. This study will be conducted in OSA patients with EDS whose EDS has not been satisfactorily treated by, or who have not tolerated OSA primary therapy. The study will be conducted by physicians specialized in sleep management such as sleep specialists, pulmonologists, cardiologists, otorhinolaryngologist and neurologists.

[figure not shown]
As an observational study, the assignment of the patient to a particular therapeutic strategy should be decided within the current clinical practice and the decision to prescribe OZAWADE® should necessarily precede and be independent of the decision to enrol the patient into the study. OZAWADE® should be prescribed and used based on the routine clinical practice as well as on the individual situation of each patient, according to the approved SmPC.

During the 2-year enrolment phase, 502 patients are planned to be recruited in four to five countries where OZAWADE® is on the market (*i.e.*, France, Germany, Italy and possibly Netherlands, Belgium or Spain), in approximately 8 to 15 centers per country.

Once eligible patients are enrolled, baseline data should be collected. Data collected in the CRF will correspond to data collected in routine practice in the investigating centers.

Patients will be followed-up up to five years, during which time they should be assessed by their treating participating physicians at 6, 12, 24, 36, 48 and 60 months, to follow routine care schedule.

Study visits, procedure and evaluations are summarized in the study flow (Figure 1) and schedule of assessments below (Table 2).

CPAP: Continuous Positive Airway Pressure; EDS: Excessive Daytime Sleepiness; FU: Follow-up; MAD: Mandibular Advancement Device; OSA: Obstructive Sleep Apnoea.

Figure 1: Study Flow.

PASS Protocol [P21-02/OZAWADE]

OZAWADE

Table 2. Schedule of Assessments

	Procedures ¹ /Visits	Inclusion	FU 6 Months	FU Year 1	FU Year 2	FU Year 3	FU Year 4	FU Year 5	End of study
	Visit window		6M [3-9M[12M [9-18M[24M [18-30M[36M [30-42M[48M [42-54M[60M [54-66M[
	Demography: age, gender	X	ē.						
	Profession / Socio-economic status	Х							
Patient interview	Height², weight	Х	Х	Х	X	X	X	X	Х
nten	Waist circumference	X	х	Х	X	X	X	х	Х

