anti	Smoking status ³	X ₃	X ³	X ³	X ₃	X ₃	X ₃	X ₃	X ³
Patie	Alcohol consumption	X	х	Х	X	X	X	X	х
	Physical activity	Х	Х	X	X	X	X	X	Х
	Relevant medical history	X							
	Prior medications (last three months)	X							
	Relevant concomitant medications	X	Х	Х	X	X	X	X	Х
e e	Physical examination	X		Х	X	X	Х	X	х
minati	All Adverse Events including adverse events of special interest ⁴		х	х	х	х	X	x	х
l exa	Blood pressure, heart rate	X	Х	Х	X	X	X	X	X
Medical examination	Biological assessment of less than 12 months (cholesterol, glycemia and triglycedemia)	х		х	х	х	х	х	Х
	ECG brought by the patient when available (QT measure) ⁵	X _e	X ⁶	X ⁶	X _e	Xe	Xe	X _e	X _e

PASS protocol Version 3.0 – 23 NOV 2023

PASS Protocol [P21-02/OZAWADE]

OZAWADE

	Procedures /Visits Visit window		FU 6 Months	FU Year 1	FU Year 2	FU Year 3	FU Year 4	FU Year 5	End of study
			6M [3-9M[12M [9-18M[24M [18-30M[36M [30-42m[48M [42-54[60M [54-66[
OSA and sleep history	OSA and sleep history, duration of sleep	X	X ⁷	Х	х	X	Х	Х	Х
	Apnoea-hypopnea index (AHI) At diagnosis of OSA At follow-up visits (with or without CPAP) ⁸	х	х	х	х	х	x	х	х
	Epworth Sleepiness Scale (ESS)	X	X	Х	Х	Х	Х	Х	Х
	CPAP or alternative (e.g., MAD) and adherence ⁹	Х	х	х	х	х	х	х	X
	Maintenance of wakefulness test (MWT) or Multiple Sleep Latency Test (MSLT)	X		х	х	X	х	х	X
	Beck Depression Inventory	Х		Х	Х	Х	Х	Х	Х
	Fatigue Severity scale	X		Х	Х	Х	Х	X	Х
	Assessment of perceived sleepiness at driving	X		х	х	х	х	х	X
OZAWADE* use	Prescription (when applicable)	X							
	Adherence with the Morisky Medication Adherence Scale 8-item (MMAS-8)		х	х	х	х	х	x	х

- 1. Data collected in the CRF will correspond to data collected in routine practice in the investigating centers.
- Height at inclusion visit only.
- 3. Smoking status: in pack-year.
- 4. Adverse events of special interest include the following cardiovascular events: acute myocardial infarction, new onset of angina, unstable angina, stroke (ischemic, haemorrhagic), transient ischemic attack, new onset atrial fibrillation, unscheduled interventional cardiology procedure (stenting, CABG), new onset hypertension (with new hypertension treatment or a posology adjustment of hypertension treatment), new onset or worsening of peripheral vascular disease or unscheduled intervention, stent thrombosis, heart failure, QT prolongation and cardiovascular death.
- 5. ECG when available.
- 6. Last test available at the time of the visit.
- 7. Duration of sleep.

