11.4. Collection and reporting of AEs, SAEs and SSs

11.4.1. Collection of the AEs, SAEs, SSs in the eCRF

The collection and reporting of AEs will follow the guidelines on Good Pharmacovigilance Practices (GVP) module VI, Revision 2.

All AEs, whether they are serious/non-serious, related/unrelated should be collected during the course of the study in the dedicated AE eCRF form. AEs will be assessed according to intensity, causality, outcome, action taken and seriousness.

SSs should be collected as AEs in the AE eCRF form whether or not they were associated with a clinical event.

AESIs should be collected as AEs in the AE eCRF form and collected as SAEs if they meet the seriousness criteria. Full details of these events must be collected in the eCRF.

For each patient, the collection period for AEs starts from the time that the patient provides consent to participate in the study/non-opposition for data collection (as foreseen by local regulation) and lasts through the end of the observation period of the study, which must include at least 28 calendar days following the last administration of OZAWADE®.

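### Table 2 sets no age limit on the ECG taken as a visit's QTcF value, so an ECG from before inclusion or before a late OZAWADE start can be entered as follow-up

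*Protocol*

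**What the plan says.** Only the protocol is at hand.

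- **Source of the ECG.** The row in Table 2 (Section 9.1.1) reads "ECG brought by the patient when available (QT measure". Its cells at inclusion and at every follow-up carry footnote 6: "Last test available at the time of the visit".
- **Section 9.3.3.** ECGs are collected at inclusion and at each follow-up visit and are read centrally. No look-back limit is given.
- **Contrast in the same table.** The laboratory row is restricted to "Biological assessment of less than 12 months", and Section 9.3.9 repeats that limit.
- **Visit windows.** The table prints "6M [3-9M[12M [9-18M[24M", so the 6-month visit may fall from month 3 and the 12-month visit from month 9. These windows date the visit; they are not said to apply to the test.
- **No obligation.** Section 9.3 states that assessments need not be performed and that only what is available is collected.
- **Late start.** Section 9.3.7.1 collects exposure at inclusion and "at follow-up visits (if not started at inclusion), with the date of prescription and the prescribed dose", so treatment may begin after inclusion.
- **Use of the data.** Section 9.7.7: "ECG results, blood pressure and heart rate will be described at each collection time by treatment group". QTcF above 450 ms is also a listed non-MACE event (Section 9.3.10) and so part of the primary endpoint (Section 9.1.2.1).

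**The concern.** A follow-up QTcF value should reflect the patient's state since the last visit and, in exposed patients, on the drug. Footnote 6 does not ensure this. A site that enters an old tracing because no newer one exists is following the protocol. Three kinds of ECG can then stand as follow-up: one from before inclusion, one from before a late OZAWADE start, and one already entered at an earlier visit.

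A reused pre-dose ECG shows a change of 0 ms whatever the drug does. Section 7.2 names QT prolongation among the cardiovascular risks in the Risk Management Plan, so a summary that hides part of a QTcF shift weakens the evidence on a risk the study was set up to examine. This is a data-collection rule, and ECG dates not captured at the time may be hard to recover later.

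**Working it through.** The protocol gives no figure to reproduce here and no ECG frequency. The calculation below shows size only; its inputs are assumptions.

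**Step 1. Share of values that predate inclusion.** Assume an ECG every K months at a random phase, unrelated to study visits. At a visit in month t the last ECG predates inclusion with probability

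f = max(0, (K − t)/K).

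| ECG every | month 3 | month 6 | month 9 | month 12 | month 24 |
|---|---|---|---|---|---|
| 6 months | 50% | 0% | 0% | 0% | 0% |
| 12 months | 75% | 50% | 25% | 0% | 0% |
| 24 months | 87.5% | 75% | 62.5% | 50% | 0% |

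Months 3 and 9 are the edges of the 6-month window, and month 9 also opens the 12-month window. With K = 24 and a year-2 visit at its earliest date, month 18, f = (24 − 18)/24 = 25%. If the ECG is done at the visit, f = 0 throughout. A patient who has no new ECG at all carries the old value through every visit; Section 9.3 allows this, but its frequency is unknown.

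**Step 2. Dilution.** With a true drug effect d and no baseline difference, the group difference shown is (1 − f) × d. For an assumed d = 5 ms and treatment from inclusion:

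- K = 6: 5 ms at month 6 and 5 ms at month 12.
- K = 12: 0.50 × 5 = 2.5 ms, then 5 ms.
- K = 24: 0.25 × 5 = 1.25 ms, then 0.50 × 5 = 2.5 ms.

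The only QTc effect in the protocol is 10–13 ms at 6 to 12 times the therapeutic dose (Section 7.1). It does not give an effect at the therapeutic dose. With f = 0.5 it would appear as 5.0–6.5 ms.

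**Step 3. Late start.** If OZAWADE starts at month s, the pre-dose share at a later visit is max(0, (K − (t − s))/K). With s = 3, t = 6 and K = 12 this is (12 − 3)/12 = 75%, against 50% for a start at inclusion.

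**Step 4. Values not new since the previous visit.** The share is 1 − min(1, interval/K), with intervals of 6, 6, 12, 12, 12 and 12 months.

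- K = 6: 0% throughout.
- K = 12: 50% at months 6 and 12, then 0%.
- K = 24: 75% at months 6 and 12, then 50%.

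At month 12 with K = 24, the 75% consists of 50% from before inclusion and 25% from between inclusion and month 6.

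**Step 5. Would the laboratory limit do?** No. With K = 12 every last ECG is at most 12 months old, yet half of those at month 6 still predate inclusion.

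**Step 6. The event definition.** In Section 9.3.10 hypertension, angina and atrial fibrillation carry a new-onset qualifier; QT prolongation does not. The same section counts events from enrolment, and Section 11.4.1 states that "the collection period for AEs starts from the time that the patient provides consent". An ECG from before consent is therefore not an event, provided its date is known. An ECG between consent and a late start lies inside the collection period. If it is presented at a later visit and dated by that visit, the event is placed in the wrong period and possibly under the wrong exposure.

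**The case against.** The strongest reply is that the effect is limited. Under the assumptions above nothing predates inclusion at nominal month 24 or later, and nothing at nominal months 6 and 12 if ECGs are six-monthly. Blood pressure and heart rate are measured at the visit and at home in the following month (Section 9.3.4), so ECG age does not reach them. ECGs are read centrally (Section 9.3.3) and events are adjudicated blind (Section 9.4). This all stands and limits the size of the point. It does not remove it, because neither safeguard is given a rule on the date of the tracing.

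A reader might go further and fault Section 9.7.7 for committing only to description by group, with "Changes from inclusion may be calculated if relevant", in a non-randomised study. The protocol does not support that as an error. The section promises no adjusted contrast, the description includes the inclusion values so any baseline gap is visible, and Section 9.7 leaves detail to an SAP that is not shown. Whether these supportive measures get a baseline-adjusted model is normally settled there.

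A second objection concerns the remedy. Discarding ECGs from before the first dose in exposed patients only, and applying this to the QTcF > 450 ms event, would remove events from one group while the same early event in a control still counted. That would favour the drug. This stands, and the remedy below is the same in both groups.

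**Conclusion.** The point holds for the ECG rule in footnote 6. As written, it lets ECGs from before inclusion, before a late start, or already used stand as follow-up QTcF values, and this pulls any drug effect on QTcF towards zero. The months 6 and 12 summaries are mainly affected, and only where ECGs are infrequent: at the nominal visits 0 to 75% of month-6 values and 0 to 50% of month-12 values would predate inclusion, for assumed ECG intervals of 6 to 24 months. The real frequency is unknown, so confidence in the size is moderate. The rule should be corrected, but it concerns a supportive safety summary.

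A reader might infer that this dilution biases the non-inferiority conclusion. The protocol does not support that: the primary objective (Section 8.1) concerns the incidence of cardiovascular events, and mean QTcF is not part of that comparison. A reader might also count old ECGs above 450 ms as spurious primary events. Sections 9.3.10 and 11.4.1 already exclude events from before enrolment or consent. The primary endpoint is touched only where a QTcF > 450 ms event is misdated.

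**What to change.** In Table 2 and Section 9.3.3:

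1. Record the date of each ECG.
2. Count an ECG as a follow-up value only if it was recorded after inclusion and after the previous study visit, with the same rule in both groups.
3. Date any QTcF > 450 ms event by the ECG, not by the visit at which it was presented.
4. Assign each follow-up ECG to the exposure status on its own date, using the prescription date collected under Section 9.3.7.1. Do not delete pre-dose events in exposed patients only.
5. Report the number of patients with an eligible ECG by group and visit.

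The cost is a date field, if the eCRF does not already have one, some protocol wording and one table of counts. No visit or test is added. The drawback is fewer QTcF values at the early visits: by the complement of Step 4, 50% of patients would have an eligible ECG at months 6 and 12 with yearly ECGs (all of them later), and 25% with two-yearly ECGs (50% later). The counts show the selection that comes from using only available ECGs; they do not remove it.
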